4.3. Study Population

The study population consists of adult female patients with diagnosis of dMMR/MSI-H recurrent or advanced endometrial cancer with recurrent disease to a previous platinum, treated within the Spanish dostarlimab EAP.

4.4. Treatment Under Observation

In this study, the treatment under observation is dostarlimab administered on day 1 of each treatment cycle until disease progression, unacceptable toxicity or patient/doctor's decision. The recommended dose for dostarlimab is 4 cycles of 500 mg every 3 weeks followed by 1000 mg every 6 weeks for all subsequent cycles.

4.5. Participant Selection

- Patients must meet all the following EAP inclusion criteria and none of the exclusion criteria to be eligible.
- Participants must have received dostarlimab (at least 1 cycle) within the Spanish EAP.

5. COLLECTED DATA AND OUTCOME MEASURES

5.1. Demographics

- Age (at dostarlimab treatment initiation within EAP)

5.2. Medical History

- Non-oncological history
- Other cancers

5.3. Endometrial Cancer History

- Initial diagnosis date
- Tumor histology (and degree of tumor differentiation for endometrioid subtype)
- Disease stage
- Recurrent or initial metastatic disease
- MMR (IHC / MSI-H / MMR genetic study/ MLH1 hypermethylation)

5.4. Endometrial Cancer Previous Treatments

- Previous surgeries
- Previous drugs (types and number of previous treatments)
- Previous radiotherapy

5.5. Baseline (pre-dostarlimab)

- ECOG
- Existence of measurable disease
- CA 125

5.6. Dostarlimab Treatment

- Start date (first dose)
- Number of cycles
- Last dose
- Number of interruptions
- End of treatment date
- End of treatment reason (toxicity, doctor's decision, patient's decision, progression or other)

5.7. Disease progression after dostarlimab

- Progression date
- Progression type

5.8. Best Response Assessment

- Radiological best overall response

- Radiological best overall response assessment date
- Number of dostarlimab cycles previous to first and best radiological response
- CA125 best overall response
- CA125 best overall response assessment date

5.9. Dostarlimab -Related Adverse Events

- Event term according to Common Terminology Criteria for Adverse Events (CTCAE) criteria
- Time from dostarlimab initiation
- Event duration
- Grade
- Action taken with dostarlimab
- Outcome

5.10. Death

- Date of death
- Cause of death

5.11. Survival Status

- Last follow-up date
- Status

5.12. Subsequent Therapies for Endometrial Cancer

- Subsequent drugs

6. SAMPLE SIZE

The study will include between 100-110 patients in total (retrospective in all cases) recruited in 50-60 sites.

The population will include all patients who received dostarlimab at least during one cycle as part of the EAP in GEICO-associated hospitals. The sample size will be based on the number of patients treated in the EAP of Spain.

There will be no formal calculation of the sample size. Most patients included in the Spanish EAP will be analyzed.

7. STANDARD OF CARE

In this retrospective observational study, patients will not be exposed to clinical interventions different from those belonging to the standard of care. There are no study-specific procedures other than the normal activities that patients would undergo if they were not participating in the study. Accessible/reachable patients will be interviewed during routine care visits and principal investigators at each site will offer them the possibility of participating in the study. This will involve reading and signing the ICF.

8. DATA COLLECTION PROCESS

8.1. Patient Information and Consent

All patients participating in the study (accessible, alive patients who can be interviewed in the hospital) will receive a Patient Information Sheet (PIS) describing, in simple language, the goals, scope, procedures and relevant implications of the study. The PIS will integrate an ICF to be signed by the patient, which is indispensable for study participation (for accessible patients). Written informed consent must be given by each accessible/reachable patient before study initiation (prior to registration of the patient in the eCRF). The PIS/ICF will include the consent of patients for the collection and analysis of their clinical data.

Data of inaccessible/unreachable patients (dead, lost, etc.) could still be used according to the permissions of ethics committees and Spanish law, regarding the use of data in retrospective studies.

8.2. Clinical Data Entry

Participating local sites (GEICO-associated hospitals with expertise in gynecological cancer management) will enter clinical data of patients in the study eCRF in order to create a multicenter database. The specific data items to be entered in the eCRF are described in an eCRF specification provided as a separate document.

It is expected that data collection for the study will take place on an ongoing basis since the first site is activated and until around 100-110 subjects have been accrued, depending on timelines of regulatory and committees' authorizations.

Considering the retrospective nature of the study, no data will be recorded prospectively. For alive patients, no data generated after the date of ICF signature will be collected.

8.3. Data Sources

Considering the retrospective nature of this study, the source of information will be the patient's medical chart. Other potential sources of data are pharmacy records, databases or electronic prescribing systems. The data to be extracted in this study which are available in the patient's medical charts will be recorded in the eCRFs. Only data obtained before study initiation (the date of the first ethics committee approval) will be extracted from the patient's medical chart in order to ensure they are retrospective in nature. Data unavailable in patients' medical charts will be mentioned in the eCRFs as "not available". The degree of detail and completeness of data extracted for this study will depend on their availability according to local clinical practice. The investigator participating in this study will revise patient's medical chart to confirm eligibility of the patient. Once it is confirmed that all selection criteria are met and informed consent is given, the investigator will proceed to extract the study data available

(previously registered) in patient's medical charts and completing the eCRF. Patient medical information obtained by this study is confidential and may only be disclosed to third parties as permitted by the informed consent form signed by the subject, unless permitted or required by law. Confidentiality standards will be maintained by coding each patient enrolled in this study through assignment of a unique subject identification number.

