1.1.2. Secondary Clinical Objectives

- To assess the effectiveness of dostarlimab in terms of investigator-assessed progression-free survival (PFS) and overall survival (OS).
- To analyze the PFS rate at 6, 12, 18 and 24 months.
- To assess the disease control rate (DCR) based on investigators' assessment using RECIST 1.1.
- To evaluate duration of treatment with dostarlimab.
- To describe the time to response to dostarlimab.
- To evaluate the safety and tolerability of dostarlimab in patients with dMMR/MSI-H endometrial advanced cancer, including immune-related adverse events of interest (irAEI).
- To evaluate Neutrophil-to-lymphocyte ratio as a potential predictive biomarker for treatment with dostarlimab.

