1.1.6. Operational Milestones

Table 2: Table of Study Milestones

Number of Patients	Around 100-110
Enrollment Rate (patients/month)	Around 35
Number of Sites	50-60
Country	Spain
Study Duration	3 months (recruitment)
FPI (date)	December 2022
LPLV (date)	March 2023
Publications and/or Other Reports	September 2023 (Clinical Study) September 2024 (Translational Study)

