3. STUDY RATIONALE

There is a paucity of real-world data of patients with EC treated with dostarlimab, something that has an especial interest considering the limited evidence available with dostarlimab (only a phase I open-label study).

Moreover, there are only some discrete published studies comparing different dMMR/MSI-H approaches in EC and there are almost not data assessing their correlation to ORR of immunotherapy. To our knowledge only one phase II trial with avelumab made a comparison of dMMR/MSI-H tested by IHC, PCR or NGS, but only 15 patients were assessed in the dMMR cohort.

In January 2021, GlaxoSmithKline opened an EAP in Spain to make dostarlimab available to eligible women with recurrent or advanced dMMR/MSI-H endometrial cancer, a clear unmet medical need for these endometrial cancer patients.

EAPs allow patients with a serious or life-threatening disease or condition who are not otherwise eligible to participate in a clinical trial and have no other comparable or satisfactory therapeutic options to access drugs, with demonstrated benefit in clinical trials, that are pending approval.

This study seeks to evaluate the efficacy and tolerability of dostarlimab in recurrent or advanced dMMR/MSI-H endometrial cancer patients treated in a real world setting within the Spanish EAP. In addition, the translational study aims to assess the efficacy according to the biomarker technique used (IHC, PCR Promega®, PCR Idylla®, or gene alteration by NGS/hypermethylation).

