4. STUDY DESIGN

4.1. Overview

This is a multicenter, retrospective, observational (non-interventional) study, in patients treated in a real-world setting within the Spanish dostarlimab EAP. The study is planned to be conducted in the Medical Oncology departments at 50-60 Spanish GEICO-associated hospitals. Its multicenter nature aims to improve the representativeness of the study population in Spain. The study would include approximately 110 patients with dMMR/MSI-H recurrent or advanced EC, that have progressed on or following prior treatment with a platinum-containing regimen, treated within the dostarlimab EAP, available in Spain from January 2021 to September 2022. The total number of participating centers and patients will be confirmed once the EAP is closed.

Patient's medical records will be screened by local clinical staff to assess for eligibility according to selection criteria. The study comprises a single study visit, in which the patient will give her informed consent to participate (when the patient is alive) and the physician will extract the study data from the patient's medical charts.

Alive patients who fulfill inclusion criteria and meet no exclusion criteria will be informed by a member of their care team about the purpose of the study, as well as about potential risks and benefits of study participation. The written informed consent form (ICF) should be signed prior to study initiation in alive patients in order to access their medical records. Deceased patients will be still included but their relatives will not be contacted. In these instances, data will be collected by members of the direct care team, unless there is a prior express order from the patient to preserve confidentiality. All eligible deceased and consenting living patients at the participating centers will be included. Data will be directly retrieved from hospital medical records and reported in the electronic Case Report Form (eCRF).

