9. STATISTICAL ANALYSIS

Statistical analyses and study reports will be developed by the Coordinating Investigator of the study in collaboration with the biostatisticians of the study Contract Research Organization (CRO). The World Programming System (WPS) platform (a SAS language software) will be used for these analyses.

All variables will be summarized separately. Depending on the type of the variable, the following statistics will be reported:

- Continuous variables: number of subjects (n), number of missings, mean, standard deviation (STD), median, standard error (SE, if needed), 25th and 75th percentiles, minimum, and maximum.
- Categorical variables: frequencies and percentages (calculated over the number of non-missing values).

In general, minimum and maximum are going to be reported using the same number of decimal places as collected in the raw data. Mean, STD, median, 25th and 75th percentiles will be reported with one additional decimal place.

Time to event data will be listed and summarized at every specified timepoint using the number patients at risk, number of patients censored, number of patients with the event, Kaplan Meier estimate (%), and the 95% confidence interval. In addition, 25th, 50% and 75th percentiles from Kaplan-Meier curves will be used.

Progression-free survival is defined as the time from the date of the first administration of dostarlimab and the occurrence of disease progression or death, whichever occurs earlier.

Overall survival is defined as the time between the start of treatment and death. Patients alive at the last follow-up will be censored for the analysis of OS.

Both PFS and OS will be analyzed using the Kaplan-Meier method. The responses (valid only for patients who have started dostarlimab with measurable disease) will be assessed following the RECIST 1.1 criteria and reported in percentages.

Further details on statistical analyses will be specified in the Statistical Analysis Plan (SAP).

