14. DATA HANDLING AND RECORD KEEPING

14.1. Study Approval and Amendments

The study and all the possible amendments will be approved by Ethics Committee before starting any data collection procedure.

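### Sections 8.1 to 8.3 disagree on the data limit, and under the 8.3 limit and the planned dates the 24-month PFS rate cannot be estimated

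*Protocol*

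**What the plan says.** Sections 1.1.2 and 4.2.2 set the objective "To analyze the PFS rate at 6, 12, 18 and 24 months". Section 9 counts PFS from the first dostarlimab dose and says "Time to event data will be listed and summarized at every specified timepoint using the number patients at risk", together with the Kaplan-Meier estimate and its 95% confidence interval.

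Two sections limit the data that may feed this estimate:

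- Section 8.3: "Only data obtained before study initiation (the date of the first ethics committee approval) will be extracted".
- Section 8.2: "no data will be recorded prospectively. For alive patients, no data generated after the date of ICF signature will be collected".

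The dates come from elsewhere. Section 3 states "In January 2021, GlaxoSmithKline opened an EAP in Spain", and section 4.1 describes the EAP as "available in Spain from January 2021 to September 2022". Section 14.1 says the study "will be approved by Ethics Committee before starting any data collection procedure", and section 12.1 requires written approval before any patient is enrolled. Section 1.1.6 plans FPI for "December 2022" and last patient last visit for March 2023. The date of first ethics approval is not given.

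The term *study initiation* also varies. Section 8.3 equates it with first ethics approval, section 8.1 ties it to registration of the patient in the eCRF, and section 4.1 leaves it undefined.

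**The concern.** The data limit decides how long each patient can be followed, and the protocol gives two. They lead to different answers for a landmark that the protocol promises. Under the stricter limit the 24-month PFS rate has no data behind it; under the looser one it has very little.

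Sites could also apply different limits, because the term that defines the stricter one has another meaning in section 8.1. The 8.3 gloss cannot hold throughout the protocol. Section 4.1 requires living patients to sign the ICF before study initiation. If that meant first ethics approval, patients would have to consent before any committee had approved the consent form, against sections 12.1 and 14.1.

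At stake are one of four PFS landmarks and the precision of a second. The same limit fixes the follow-up available for duration of response and OS.

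**Working it through.** The protocol has no sample-size or precision calculation to reproduce. The check is calendar arithmetic, followed by an illustration of numbers at risk. A month is 365.25/12 = 30.44 days.

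**Step 1. Maximum follow-up under 8.3.** Every unstated date is taken at its most favourable: first dose on 1 January 2021 (the EAP opened that month, and section 4.5 requires dosing within it) and first approval on the last day of the planned FPI month.

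| First ethics approval | Days from 1 Jan 2021 | Months |
|---|---|---|
| 30 Sep 2022 | 637 | 20.93 |
| 30 Nov 2022 | 698 | 22.93 |
| 31 Dec 2022 | 729 | 23.95 |

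Twenty-four months is 730.5 days, or by calendar 1 January 2023. No date in the table reaches it, so the number at risk is zero whatever the accrual pattern or PFS. If the longest-followed patient is censored, the Kaplan-Meier curve is undefined at 24 months. If she has an event, the curve falls to zero, which is not a usable estimate.

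**Step 2. Illustrative numbers at risk.** Assumptions: N = 105 (midpoint of the 100-110 in section 6), and entry over the 638 days from 1 January 2021 to 30 September 2022. PFS is taken from the earlier dMMR cohort in section 2.4.2: 46.4% at 12 months and 40.1% at 24 months. Log-linear interpolation gives S(18) = √(0.464 × 0.401) = 0.431, and S(24) = 0.401.

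Expected number at risk at time t = N × F(x) × S(t), with x = (cut-off day − t in days)/638, held between 0 and 1. F(x) = x for uniform entry, x² for a linearly rising entry rate, and 2x − x² for a linearly falling one.

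*24 months under the 8.2 limit alone:*

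- All ICFs signed on 31 March 2023 (day 819): x = (819 − 730.5)/638 = 0.139, and 105 × 0.139 × 0.401 = 5.8. Rising to falling entry gives 0.8 to 10.9.
- ICFs spread evenly from 1 December 2022 to 31 March 2023: 2.2. Rising to falling entry gives 0.2 to 4.1.

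*18 months (547.9 days) under the 8.3 limit:*

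| First ethics approval | x | Uniform | Rising to falling |
|---|---|---|---|
| 30 Nov 2022 | (698 − 547.9)/638 = 0.235 | 10.7 | 2.5 to 18.8 |
| 31 Dec 2022 | (729 − 547.9)/638 = 0.284 | 12.9 | 3.7 to 22.1 |

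Using N = 100 or 110 changes each count by about 5%.

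**The case against.** **Section 8.2 may be the intended limit.** Its sentence on ICF signature would do nothing if 8.3 governed, and the 8.3 parenthesis may be a slip. This stands in part. A reader might infer that the 24-month rate is impossible on any reading; the documents do not support that, because under 8.2 alone an estimate could exist. But nothing in 8.2 lifts the 8.3 limit. Applied together, the earlier limit binds.

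**The dates are plans and the margin is one day.** Section 8.2 makes data collection depend on authorisation timelines, and first approval in 2023 would change the result. The conclusion is therefore limited to the planned dates. The one-day margin needs a first dose on the first possible day and first approval on the last day of the FPI month; any realistic gap widens it. A 30-day-month convention (720 days) would admit only patients dosed in the first days of January 2021.

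**The 18-month rate is not empty.** A reader might infer that it too could rest on nobody, since approval by 1 July 2022 (17.94 months) would give that result. The documents do not support leaning on this. The EAP ran to September 2022, and everyone with at least one cycle is included. A limit of 1 July would leave patients who started from then until September with no extractable dostarlimab data. Approval close to the planned FPI leaves roughly 11 to 13 at risk, which is few but estimable.

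**The counts borrow from another cohort.** That cohort required measurable disease and used blinded central review. This study uses investigator assessment and does not require measurable disease. The objection stands: the counts show scale only. The zero under 8.3 does not use them.

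**The endpoint is secondary.** This also stands. The study is descriptive, and a missing landmark would normally be reported as not estimable. A statistical analysis plan, however, cannot create follow-up that the protocol forbids extracting.

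**Conclusion.** The point holds in this form. Sections 8.2 and 8.3 set different data limits, and sections 4.1, 8.1 and 8.3 do not share one meaning of study initiation. Under the 8.3 limit and the planned dates, follow-up is at most 23.95 months and the 24-month PFS rate cannot be estimated. That result rests only on the EAP opening date, the rule that approval comes first, and FPI in December 2022. Under the 8.2 limit alone the rate would rest on a handful of patients, about 2 to 6 with uniform entry. The 18-month rate is estimable with late-2022 approval, from about 11 to 13 patients on the same assumptions; the entry pattern moves these counts widely.

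A reader might infer that the primary objective fails. It does not: ORR does not depend on the 24-month landmark. This is worth correcting before extraction begins, but it does not threaten the study.

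**What to change.** 1. State one calendar data cut-off in sections 8.2 and 8.3, on or before the first ICF signature, and apply it identically to living, deceased and unreachable patients. Section 8.2 is then met automatically and the design stays retrospective. A later date would not do. Living patients would stop at consent while deceased patients contributed events up to the later date, so follow-up would depend on vital status.
2. Use *study initiation* with one meaning in sections 4.1, 8.1 and 8.3.
3. Remove the 24-month PFS rate from sections 1.1.2 and 4.2.2, or report it only if the chosen cut-off leaves patients at risk at 24 months. With the first signature planned for December 2022, a cut-off under item 1 leaves none.
4. Keep the 18-month rate and show the number at risk beside it.

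The cost is an amendment of wording, which needs ethics approval under section 12.1. The study also gives up a 24-month figure that its planned dates do not support.

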8.4. Limitations of the Research Method

This is a retrospective study designed to extract information already obtained in an EAP clinical practice of the participating sites that is registered in patients' medical chart. The main limitation of this study therefore arises from the obvious limitations of a retrospective chart review that uses existing medical data recorded for reasons other than research, including incomplete or unrecorded documentation. The validity of study results will therefore be limited by the information available and the presence of missing data.

Nevertheless, it is expected that most data to be collected in this study will be available as they are routinely registered in the medical charts of the target population.

So, the information obtained in this study regarding safety data must be considered with caution given that these came from a retrospective review of medical charts where it is likely that information on adverse events may have been under recorded in comparison with a prospective and controlled clinical trial setting. In addition, safety results must be interpreted within the context of the current safety management systems in the participating hospitals.

9. STATISTICAL ANALYSIS

Statistical analyses and study reports will be developed by the Coordinating Investigator of the study in collaboration with the biostatisticians of the study Contract Research Organization (CRO). The World Programming System (WPS) platform (a SAS language software) will be used for these analyses.

All variables will be summarized separately. Depending on the type of the variable, the following statistics will be reported:

- Continuous variables: number of subjects (n), number of missings, mean, standard deviation (STD), median, standard error (SE, if needed), 25th and 75th percentiles, minimum, and maximum.
- Categorical variables: frequencies and percentages (calculated over the number of non-missing values).

In general, minimum and maximum are going to be reported using the same number of decimal places as collected in the raw data. Mean, STD, median, 25th and 75th percentiles will be reported with one additional decimal place.

Time to event data will be listed and summarized at every specified timepoint using the number patients at risk, number of patients censored, number of patients with the event, Kaplan Meier estimate (%), and the 95% confidence interval. In addition, 25th, 50% and 75th percentiles from Kaplan-Meier curves will be used.

Progression-free survival is defined as the time from the date of the first administration of dostarlimab and the occurrence of disease progression or death, whichever occurs earlier.

Overall survival is defined as the time between the start of treatment and death. Patients alive at the last follow-up will be censored for the analysis of OS.

Both PFS and OS will be analyzed using the Kaplan-Meier method. The responses (valid only for patients who have started dostarlimab with measurable disease) will be assessed following the RECIST 1.1 criteria and reported in percentages.

Further details on statistical analyses will be specified in the Statistical Analysis Plan (SAP).

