2.4.2. Clinical Experience

The efficacy and safety of dostarlimab were investigated in GARNET (Study 4010-01-001), a multicenter, non-randomized, multiple parallel cohort, open label study conducted in patients with advanced solid tumors.

The recruitment began in March 2016 and the trial was conducted in 2 parts. Part 1 was a dose-escalation study to evaluate weight-based doses of dostarlimab. Part 2A evaluated the safety of non weight-based fixed doses of dostarlimab, while part 2B enrolled patients into several expansion cohorts based on tumor type and MMR status (regarding EC, cohort A1 included patients with dMMR tumors, and cohort A2 included patients with pMMR tumors) to assess the antitumor activity and safety of dostarlimab.

Part 1 employed a modified 3 + 3 design to evaluate ascending weight-based doses of intravenous infusion. Part 2A assessed the safety and tolerability of two fixed doses of

dostarlimab. No dose-limiting toxicities were observed, and the recommended therapeutic dose was determined to be 500 mg every 3 weeks for the first 4 cycles followed by 1000 mg every 6 weeks for all subsequent cycles, based on the efficacy, safety, receptor occupancy (fully occupied at all dose levels), and pharmacokinetics analysis. This dosing schedule was selected for part 2B.

In expansion A1 cohort of part 2B eligible patients had recurrent or advanced dMMR/MSI-H EC, with measurable disease that had progressed after a platinum-containing chemotherapy regimen (administered in the adjuvant setting or for the advanced disease) and were to have received no more than 2 lines of therapy for advanced or recurrent disease. The primary objective of the A1 cohort analysis was to evaluate the antitumor activity of dostarlimab by assessing the ORR by blinded independent central review (BICR) using RECIST v1.1, and DOR.

The secondary endpoints included the following: 1) DCR, defined as the proportion of patients with an objective response or stable disease lasting 12 weeks or longer, based on BICR using RECIST 1.1 criteria; 2) immune-related ORR (irORR) and immune-related DOR (irDOR) based on the investigator assessment using immune-related RECIST (irRECIST); 3) PFS, based on BICR using RECIST 1.1; 4) immune-related PFS, based on the investigator assessment using irRECIST; and 5) OS.

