4.2. Study Objectives

4.2.1. Primary Clinical Objective

- To assess the antitumor activity of dostarlimab in patients with recurrent or advanced mismatch repair deficient (dMMR)/microsatellite instability-high (MSI-H) endometrial cancer, in terms of objective response rate (ORR) and duration of response (DOR) based on investigators' assessment using Response Evaluation Criteria in Solid Tumors (RECIST) v1.1.

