APPENDIX 3. DOSTARLIMAB EAP INCLUSION/EXCLUSION CRITERIA

Inclusion Criteria

To be considered eligible to participate in this program, all of the following requirements must be met:

1. At least 18 years of age, able to understand the program procedures and agree to participate by providing written informed consent.
2. Histologically diagnosed endometrial cancer (note: all histologies are permitted except endometrial sarcoma [including carcinosarcoma]).
3. Patient has evidence of tumor DNA damage repair dysfunction (dMMR/MSI-H) via locally available, validated methodology.
4. Patient has progressed on or after platinum containing chemotherapy (and has received no more than 2 lines of anti-cancer therapy for recurrent or advanced (Stage \geq IIIB) disease (first or second line)); prior treatment with hormone therapies is acceptable and does not count towards the number of lines of therapy.
5. ECOG performance status of ≤ 2 .
6. Adequate organ and bone marrow function, as defined below:
 - a. Absolute neutrophil count (ANC) $\geq 1,500/\mu\text{L}$
 - b. Platelets $\geq 100,000/\mu\text{L}$
 - c. Hemoglobin ≥ 9 g/dL
 - d. Adequate liver and renal function:
 - Serum creatinine $\leq 1.5 \times$ upper limit of normal (ULN) or calculated creatinine clearance ≥ 50 mL/min using Cockcroft-Gault equation for patients with creatinine levels $> 1.5 \times$ institutional ULN.
 - Total bilirubin $\leq 1.5 \times$ ULN AND direct bilirubin $\leq 1 \times$ ULN.
 - Aspartate aminotransferase (AST) and alanine aminotransferase (ALT) $\leq 2.5 \times$ ULN unless liver metastases are present, in which case they must be $\leq 5 \times$ ULN.
7. Cannot be satisfactorily treated with available alternative treatments.
8. Not eligible for a clinical trial with dostarlimab within the indication of the EAP (where access to the clinical trial site is possible).

9. A female participant is eligible to participate if she is not pregnant or breastfeeding, and if one of the following conditions applies:

- Is a woman of non-childbearing potential (WONCBP)

OR

- Is a WOCBP and using a contraceptive method that is highly effective (with a failure rate of < 1 % per year), preferably with low user dependency, during treatment and for at least 4 months after treatment. The treating physician should evaluate the potential for contraceptive method failure (e.g., noncompliance, recently initiated) in relationship to the first dose of dostarlimab.

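### The primary ORR denominator rests on one retrospectively abstracted measurable-disease item with no listed pre-dose scan date, so outcome-related exclusion is possible and could not be checked

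*Protocol*

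**What the plan says.** The primary objective (Protocol 4.2.1) is antitumour activity "in terms of objective response rate (ORR) and duration of response (DOR) based on investigators' assessment", under RECIST 1.1. Section 9 then limits the response analysis: "The responses (valid only for patients who have started dostarlimab with measurable disease". It also says that categorical percentages are taken over non-missing values, and it leaves further detail to an SAP.

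The variable that decides membership is listed in Section 5.5, under a pre-dostarlimab heading, as "Existence of measurable disease". Sections 5.3 to 5.10 list dates for diagnosis, first dose, end of treatment, progression, best response and death. They list none for the baseline tumour assessment, and no lesion data.

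Measurable disease is not required for entry. Section 4.5 asks for the EAP criteria plus treatment: "Participants must have received dostarlimab (at least 1 cycle) within the Spanish EAP". The disease criteria in Appendix 3 cover histology, dMMR/MSI-H status and prior therapy ("Patient has progressed on or after platinum containing chemotherapy"), but not measurability. By contrast, Section 2.4.2 describes the earlier dostarlimab dMMR cohort as enrolling patients "with measurable disease that had progressed after a platinum-containing chemotherapy regimen".

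Section 4.1 has the physician extract all data from the chart at a single study visit. On completeness, Section 8.3 says: "The degree of detail and completeness of data extracted for this study will depend on their availability according to local clinical practice". Items absent from the chart are entered as not available.

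**The concern.** When measurable disease is an entry criterion, the response denominator is settled before treatment and cannot depend on what happens later. Here the protocol contains no such step. Who counts in the primary denominator is coded from the chart by someone who can also see, and who reports, the response. If a patient with vague baseline imaging and a poor outcome is coded as having no measurable disease, she leaves the denominator and takes no responder with her, so ORR rises.

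The missing-value rule is a second route in the same direction. If it is applied to best response, a patient with measurable disease who died or deteriorated before a scan would have no response value and would drop out of the percentage. Section 9 states no exception for response.

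At stake is the credibility of the primary estimate. Without the date of the pre-dose assessment, a later reader cannot confirm that the classification rests on a scan made before the first dose.

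**Working it through.** **Figures to reproduce.** Section 6 states that there is no formal sample size calculation, so there is no power or precision figure to check. As a check on method, exact (Clopper-Pearson) intervals reproduce the ORRs quoted for the earlier cohort in 2.4.2:
- 30/71 = 42.3% (30.6 to 54.6)
- 65/143 = 45.5% (37.1 to 54.0), where 65 is 45.5% of 143, rounded

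**Lag between treatment and abstraction.** Section 4.1 gives EAP access as January 2021 to September 2022. Table 2 places the study visits between December 2022 and March 2023. The longest lag is January 2021 to March 2023, 26 months. The shortest is September 2022 to December 2022, 3 months.

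**Effect of outcome-related miscoding.** Let n be the truly measurable patients, x the responders, p = x/n, and k the non-responders wrongly coded as not measurable. Then ORR = x/(n − k), and the shift is p × k/(n − k).

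Assumed inputs (the documents give no count of measurable patients): 105 treated, within the planned 100 to 110; n = 90; x = 41.

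| k | ORR | Shift (points) |
|---|---|---|
| 0 | 41/90 = 45.6% (exact 95% CI 35.0 to 56.4) | 0 |
| 3 | 41/87 = 47.1% | 45.56 × 3/87 = 1.6 |
| 5 | 41/85 = 48.2% | 45.56 × 5/85 = 2.7 |
| 10 | 41/80 = 51.3% | 45.56 × 10/80 = 5.7 |

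The half-width of the k = 0 interval is (56.4 − 35.0)/2 = 10.7 points. Every shift in the table is smaller than the sampling uncertainty, but all go one way.

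**Other assumed sizes.** With 110 patients all truly measurable and 50 responders (45.5%), removing 6 non-responders gives 50/104 = 48.1%, and removing 11 gives 50/99 = 50.5%. Removing 22 gives 50/88 = 56.8%, but that would miscode 22 of the 60 non-responders and is an extreme.

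**If coding is unrelated to response.** Removing k patients at random removes k × p responders on average. Then (x − kp)/(n − k) = p(n − k)/(n − k) = p, so the expected ORR does not move. Only coding related to outcome biases it.

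**All-treated figure.** 41/105 = 39.0%. The gap of 45.6 − 39.0 = 6.6 points arises because 15 assumed non-measurable patients are counted as non-responders. It is a difference in population, not a bias.

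**The case against.** The restriction is not an error. The earlier cohort also required measurable disease, so the same restriction here helps comparability, and Section 9 states it openly. This stands.

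The item is labelled as pre-dostarlimab and must come from information already in the chart, under RECIST 1.1. It is therefore not a free judgement, and its absence from the entry criteria does not show that no baseline scan was made. An abstractor who knows the outcome is inherent in chart review. This also stands, and it is why the point concerns what can be verified and alleges no misconduct.

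Section 8.2 refers to a separate eCRF specification, and Section 9 to an SAP. Either may hold a scan date or further analyses. In part this stands: exclusion counts and a repeat analysis by scan window are ordinary SAP content and are not asked for here. But Section 5 is the protocol's own list of collected data and gives dates for the other key events. If the baseline date is not collected at the single chart visit, no SAP can recover it.

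A reader might infer that non-responders would vanish unseen. The documents do not support that. Section 9 summarizes all variables, so the number without measurable disease would appear, and outcomes could be tabulated by that item. Only the dependence of the coding on response would stay hidden. A reader might also infer that coding always happens years afterwards; the lag runs from about 3 to 26 months. Nor do the documents say anything about how old baseline scans were, so an effect of stale scans is conjecture.

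**Conclusion.** The point holds as a gap in verification and not as demonstrated bias. Measurable disease defines the primary denominator, was not required at entry, rests on one item with no listed pre-dose assessment date, and is abstracted with the outcome in view. The non-missing rule can remove further patients for reasons related to outcome.

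Under the assumed 41 responders among 90 measurable patients, miscoding 3 to 10 non-responders adds about 1.6 to 5.7 points to ORR, within the interval's half-width of 10.7. The counts are illustrative, and so is the direction: both rest on miscoding falling only on non-responders. The 39.0% over all treated patients must not be read as the unbiased value or added to the miscoding effect.

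The primary estimate remains usable. The change is worth making because it is cheap and lets a reader check the denominator.

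**What to change.** In Section 5.5, add the date of the last tumour assessment before the first dose, and state that measurable disease is coded from that pre-dose radiology report.

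In Section 9, keep ORR in patients with measurable disease as the primary analysis. State that measurable patients without a recorded response assessment count as non-responders and are not dropped as missing. Report beside it an ORR over all treated patients, with non-measurable or unknown status counted as non-response, and label it as a different population.

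The cost is one additional eCRF date, a few sentences in Section 9, and a companion figure that will look less favourable than the primary. No new patient procedure is needed.
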